7. BACKGROUND AND SIGNIFICANCE

Following painful surgical procedures of the breast, postoperative analgesia is often provided with a paravertebral nerve block (PVB). For intense, but shorter-duration acute pain, a single-injection of local anesthetic is used with a duration of approximately 12 hours. The PVB has several limitations: it can decrease blood pressure, and very rare—but serious—complications have occurred, including

neuraxial injection, neuraxial hematoma, and pleural puncture.¹ An alternative block has been described: the Pecs-2 block.² The theoretical benefits include ease of administration since it is a plane superficial to the PVB and therefore easier to identify and target with ultrasound (therefore increasing success rate); and an increased safety margin: there are few anatomic structures in the immediate area which could be injured with the needle.³ To date, 7 randomized trials involving Pecs-2 block have been published, all involving mastectomy and a placebo control, and concluded that the Pecs-2 block does, in fact, provide post-mastectomy analgesia compared with a placebo control.⁴ Six of 7 studies reported no related adverse events. In one trial the occurrence of a hematoma and/or bleeding in three patients (2%) was reported, but it was unclear if these were related to the nerve block or a surgical complication. Of note, our proposed study includes subjects having breast surgery other than mastectomy, which has not been previously investigated (and also uses an active control—the paravertebral block—compared with placebo controls). Lastly, the plane may be easier to catheterize for continuous peripheral nerve blocks relative to the relatively-small volume PVB.⁵

There are therefore multiple *theoretical* reasons to prefer the Pecs-2 block. Unfortunately, it remains unknown if the analgesia provided by this new technique is comparable to that provided with the PVB.¹ We therefore propose to compare these two techniques with a randomized, subject-masked, active-controlled, parallel-arm, human subjects clinical trial.

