9. RESEARCH DESIGN AND METHODS

This investigation will be a randomized, subject-masked, active-controlled parallel-arm, human subjects clinical trial. Of note, we will be using standard-of-care local anesthetic under an FDA-approved purpose and do not plan to research a possible change of indication or use of these medications as part of this research project. The treatments in both groups are currently used at our institution and there is true clinical equipoise at this time. The only difference in treatment between subjects who enroll versus those not enrolled in this study will be those who enroll will have the decision between which anatomic block location determined randomly, as opposed to the physician simply choosing him/herself.

Enrollment. Consenting adults undergoing breast surgery with a planned single-injection regional analgesic will be offered enrollment. Patients undergoing breast surgery with a planned perineural catheter regional analgesic will be excluded. Study inclusion will be proposed to eligible patients prior to surgery. If a patient desires study participation, written, informed consent will be obtained using a current UCSD IRB-approved ICF. Selection for inclusion will not be based on gender, race, or socioeconomic status. The study population of interest includes men and women of all races and socioeconomic status. Inclusion and exclusion criteria are listed in section #9 below.

Preoperative Procedures. Following written, informed consent, we will collect baseline anthropomorphic information (e.g., age, sex, height, and weight). All subjects will have a peripheral intravenous (IV) catheter inserted, standard noninvasive monitors applied, supplemental oxygen administered via a nasal cannula or face mask, and placed in the sitting position. Midazolam and fentanyl (IV) will be titrated for patient comfort, while ensuring that patients remain responsive to verbal cues. Both possible block locations will be viewed with ultrasound. If one or both of the locations is unacceptable for block placement in the clinician's opinion, the subject will not be

randomized and will not proceed further with the study.

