Subjects will then be randomized using a computer-generated list and opaque, sealed envelopes to one of two treatment groups: (blocks of 4, stratified for unilateral vs. bilateral surgery): (1) Pecs-2 or (2) paravertebral block. All blocks will be placed by a regional anesthesia fellow or resident under the direct supervision and guidance of a regional anesthesia attending (or by the attending themselves).

For paravertebral blocks, a total of 18 mL of ropivacaine 0.5% with epinephrine will be administered per side (90 mg). An equivalent mass of ropivacaine will be administered for the Pecs-2 blocks (90 mg), but since more volume is required (30 mL per treated side), the concentration will be decreased to 0.3% ropivacaine (with epinephrine). Therefore, for bilateral procedures, 90 mg will be administered bilaterally. The area of needle insertion will be cleaned with chlorhexidine gluconate and isopropyl alcohol. All blocks will be placed using standard UCSD ultrasound-guided techniques as previously described.³

For Pecs-2 blocks and as described by Bashandy and Abbas,³ the needle will be advanced to the tissue plane between the pectoralis major and minor muscles at the vicinity of the pectoral branch of the acromiothoracic artery where 10 mL of local anesthetic will be deposited (Figs. 1-4). In a similar manner, 20 mL will be deposited at the level of the third rib above the serratus anterior muscle with the intent of spreading injectate to the axilla.

For paravertebral blocks, ropivacaine 0.5% 9 mL will be administered at each of two levels per side: the T3 and T5 levels for sides without axillary involvement; and at the T2 and T4 level for sides with axillary involvement.

[figure not shown]

FIGURE 1. Image of the probe position and needle direction from medial to lateral during Pecs I block.³⁰

FIGURE 2. Pecs I block ultrasound view. ax.a indicates axillary artery; p., pectoral branch of thoracoacromial artery.

FIGURE 3. Ultrasound image of needle tip at the plane of Pecs I block between the 2 pectoral muscles (arrows indicate the needle).³⁰

FIGURE 4. Local anesthetic spread between the 2 pectoral muscles. The arrow is pointing to the needle. LA indicates local anesthetic.

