Single-injection blocks will be considered successful if, within 30 minutes, the subject experiences decreased sensation to cold temperature with an alcohol pad over the approximate level of the ipsilateral 4th thoracic dermatome. Misplaced blocks will be replaced successfully, or the patient excluded from further study participation. For subjects undergoing bilateral surgical procedures, a block using the same protocol will be administered on the contralateral side.

Intraoperatively, all subjects will receive a general anesthetic using inhaled and intravenous anesthetic and oxygen. Intravenous fentanyl will be administered for cardiovascular responsiveness to noxious stimuli at the discretion of the anesthesia provider.

Postop: Subjects will be discharged with a prescription for oxycodone 5 mg tablets for supplementary analgesia and instructed to record the time at which they take their first opioid tablet as well as the time at which they believe the block starts to wear off.

Outcome measurements (end points). Pain scores will be recorded using the NRS. Within the recovery room, pain scores, opioid requirements, and antiemetic administration will be recorded by nursing staff masked to treatment group. The morning following surgery, all subjects will be contacted by phone or in person [if hospitalized] to record lowest, average, highest, and current pain scores; sleep disturbances, and nausea using a 0-10 Likert scale (0 = no nausea; 10 = vomiting). For outpatients, opioid requirements will be recorded while inpatients will have opioid requirements extracted from the electronic medical record. In addition, we will extract antiemetic use from the electronic record. We will collect the times at which subjects felt their block resolve and they consumed their first opioid analgesic pills following recovery room discharge.

Hypothesis 1: Following breast surgery, **analgesia** will be non-inferior in the recovery room with a Pecs-2 block compared with a paravertebral block as measured with the Numeric Rating Scale.

Hypothesis 2: For breast surgery, **opioid** consumption will be non-inferior in the operating and recovery rooms with a Pecs-2 block compared with a paravertebral block (primary: cumulative intravenous morphine equivalents).

Primary end point: *In order to claim that Pecs-2 blocks are non-inferior to paravertebral blocks, both Hypotheses 1 and 2 must be at least non-inferior.*

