Statistical methods. Descriptive statistics will be provided by arm and in aggregate. Baseline characteristics of arms will be compared using the Wilcoxon-Mann-Whitney and Fisher's Exact tests. Key characteristics that are significantly different ($p < 0.05$) will be included as covariates in the analysis models.

Primary aim. We will test the noninferiority of the serratus nerve block compared to the paravertebral nerve block. The 95% confidence interval (CI) associated with the Wilcoxon-Mann-Whitney test will be derived for the group difference (paravertebral minus serratus) in median pain scores within the recovery room. If the lower limit of the 95% CI is greater than -1.25, we will conclude noninferiority. If there are significant differences between the groups in any key characteristics, these characteristics will be included as covariates in a linear model. The same noninferiority margin (-1.25) will be applied to the 95% CI for the covariate adjusted group difference in mean pain derived from the linear model.

The noninferiority of the serratus nerve block with regard to total opioid consumption within the operating and recovery rooms will be tested in the same manner as pain, i.e. comparing the limits of a 95% CI associated with the Wilcoxon-Mann-Whitney test to a predefined noninferiority margin (in this case 2 mg). Covariate adjusted linear models will again be applied in the event that key characteristics are significantly different between the groups.

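### A randomised subject whose misplaced block is not successfully replaced leaves the study before the primary outcomes are complete, and no analysis set keeps that subject

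*Combined protocol and SAP*

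**What the plan says.** All of this is in section 9 (Research Design and Methods) unless noted.

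- **Before randomisation.** "Both possible block locations will be viewed with ultrasound", and a subject with an unacceptable site is not randomised.
- **Randomisation.** "Subjects will then be randomized using a computer-generated list and opaque, sealed envelopes". Only then is the block placed, by a trainee "under the direct supervision and guidance of a regional anesthesia attending" or by the attending.
- **Block test.** "Single-injection blocks will be considered successful if, within 30 minutes, the subject experiences decreased sensation to cold temperature", tested at about the fourth thoracic dermatome.
- **Exclusion rule.** "Misplaced blocks will be replaced successfully, or the patient excluded from further study participation".
- **Primary outcomes.** These are recovery-room NRS pain, and opioid use in the operating and recovery rooms. Noninferiority is needed on both, with pain tested first.
- **Analysis.** "The 95% confidence interval (CI) associated with the Wilcoxon-Mann-Whitney test will be derived for the group difference" in recovery-room pain, with a margin of 1.25 points. Opioid use is handled the same way with a margin of 2 mg. No intention-to-treat, modified or per-protocol set is named, and no sensitivity analysis is planned.
- **Sample size.** The target is 75 per group, 150 in all, counting subjects who have primary end point values. Enrolment is capped at 175 to cover dropouts.

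On block performance, section 7 (Background and Significance) says of Pecs-2: "The theoretical benefits include ease of administration since it is a plane superficial to the PVB". A higher success rate is listed there only as part of that theoretical case. Section 9 says that "there is true clinical equipoise at this time".

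**The concern.** The exclusion happens after allocation and is triggered by the result of the allocated treatment. Successful placement is part of what distinguishes the two techniques, so removing failures takes that part out of the comparison. Those who remain are no longer the groups that randomisation formed.

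If failed blocks hurt more and fail at different rates, dropping them flatters the technique that fails more. The noninferiority claim becomes easier to reach if Pecs-2 fails more, and harder if the paravertebral block does. Because no analysis set is named, the choice could also be made after the data are seen.

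The sample-size wording does not settle this. A target that counts only subjects with end point data suggests that excluded subjects are replaced by new ones and not analysed. Exclusion from further participation might still allow outcomes to be taken from records, but the plan describes no such follow-up.

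**Working it through.** **1. Order of events.** Ultrasound check → randomisation → block → cold test within 30 minutes → replacement or exclusion → surgery (operating-room opioid) → recovery room (pain and opioid). The exclusion falls after allocation and before either outcome is complete. This conclusion needs no figures.

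**2. The plan's own power.** Pain inputs from the sample size paragraph are median 3, quartiles 2 and 5, the same distribution in both arms, and margin 1.25. The reading used here puts 25% of subjects on each of scores 0–2, 3, 4–5 and 6–10, uniform within each band.

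- Mean = 0.25 × (1 + 3 + 4.5 + 8) = 4.125.
- Noninferiority is declared if the lower 95% Wilcoxon-Mann-Whitney limit for paravertebral minus Pecs-2 exceeds −1.25. (The statistical text calls the test block serratus; I read this as Pecs-2.)
- At 50 per arm, 10,000 simulated trials give 80.3%, or 81.1% with tie correction. The plan states 82%, so it is reproduced to within 2 points.
- At 75 per arm with no failures, the result is 93.6%.

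**3. Assumed effect of a failed block.** The documents give neither a failure rate nor an outcome after failure, so both are assumptions. A failed block in either arm adds 3 points, capped at 10.

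- Mean after failure = 0.25 × (4 + 6 + 7.5 + 9.8) = 6.825.
- Actual increase = 6.825 − 4.125 = 2.70.
- If successful blocks are equal, the all-randomised mean difference (paravertebral minus Pecs-2) = (paravertebral failure rate − Pecs-2 failure rate) × 2.70.

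**4. Chance of the pain noninferiority claim.** 75 randomised per arm, 200,000 simulated trials per row, both analyses run on the same trials.

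| Failures, Pecs-2 v paravertebral | True mean difference, all randomised | All kept | Failures excluded |
|---|---|---|---|
| 2% v 0% | −0.02 × 2.70 = −0.054 | 91.6% | 93.4% |
| 5% v 0% | −0.05 × 2.70 = −0.135 | 88.0% | 93.0% |
| 0% v 5% | +0.05 × 2.70 = +0.135 | 96.1% | 93.0% |
| 10% v 10% | 0 | 90.9% | 90.9% |

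A 5% rate in one arm is 0.05 × 75 = 3.75, or about four subjects. Rows 2 and 3 show the direction reversing with the arm that fails more.

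**5. Sensitivity.** At 5% v 0%, adding 2 points instead of 3 gives 89.9% v 92.9% (all kept v excluded), and adding 4 gives 86.0% v 93.0%. Simulation error is negligible: √(0.88 × 0.12 / 200,000) is about 0.0007. The choice of distribution matters more, since other readings of the quartile description give 87–88% at 50 per arm.

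**6. Keeping everyone is not always the stricter analysis.** Suppose successful Pecs-2 blocks are 1 point worse (0.95 on average after the cap at 10) and failed blocks hurt alike, with 10% failures in each arm. The all-randomised difference is −0.9 × 0.95 = −0.855, against −0.95 among successful blocks. The claim is reached in 32.7% with all kept and 26.5% with failures excluded. Shared failures dilute a real difference, which is why a successful-block analysis is worth showing.

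**7. Opioid.** With the plan's truncated normal (mean 2.5 mg, SD 2 mg, minimum 0), margin 2 mg and an assumed 3 mg per failed block, the claim is reached at least 99.9% of the time either way if successful blocks are equal.

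**The case against.** The best defence is that few subjects will meet the rule. It takes a site judged acceptable on ultrasound, an attending-supervised or attending-placed block, misplacement, and then unsuccessful replacement. At 2% v 0% the two analyses differ by 93.4 − 91.6 = 1.8 points, and at 10% in each arm with equal successful blocks they do not differ. This limits the likely size. It does not supply an analysis set or make the exclusion independent of the assigned block.

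Four stronger readings are tempting, and the documents do not support them.

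- **The rule is biased towards Pecs-2.** The only hint about failure points the other way: a higher Pecs-2 success rate is named as a theoretical benefit. If that were true, exclusion would work against Pecs-2. The direction is open.
- **The false-claim rate is inflated by a known amount.** Every scenario above has a true mean difference inside the 1.25 margin, so the percentages show how often a claim that is true on the mean scale is reached. A false-claim figure would need an assumed true difference at the margin and an assumed part of it hidden by exclusion. The documents give neither.
- **The dropout allowance bounds the failure rate.** 25/175 = 14.3% covers all losses in both arms. If all 25 fell in one arm of about 87, that would be 25/87, about 29%.
- **Every failed cold test leads to exclusion.** The exclusion sentence follows the success definition, but the plan does not say that a misplaced block means a failed cold test. Poor pain relief after a block that passes the test stays in the data.

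It is also fair to say that requiring two analyses to agree goes beyond curing an unstated analysis set. I accept that and do not ask for it.

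**Conclusion.** The point stands as a should-fix matter. The plan contains a stated post-randomisation exclusion that depends on the performance of the assigned block, and nothing in the analysis text restores those subjects. It is therefore more than a missing detail: applied as written, it can bias the comparison.

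Size and direction cannot be fixed from the documents. Under the stated assumptions, the effect on the chance of the pain claim is about 2 points at 2% v 0% failures and 5 points at 5% v 0%. It reverses if the paravertebral block fails more, and is nil at 10% in each arm when successful blocks are equal. These figures depend on an assumed 3-point penalty and on one reading of the pain distribution. The plan's power figures are not in question.

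**What to change.** 1. Leave the clinical handling of a failed block as it is, but state that it does not end study follow-up or analysis.
2. Collect recovery-room NRS and operating- and recovery-room opioid use for every randomised subject.
3. Make the primary analysis all randomised subjects by assigned block.
4. Report a successful-block (per-protocol) analysis beside it as supporting, and discuss any disagreement.
5. State for reporting what counts as misplaced, and give misplaced, replaced and unreplaced blocks by arm.
6. Count these subjects towards the 150 with end point data.

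The cost is wording and one extra analysis. Masked nurses already record recovery-room pain and opioid use; operating-room opioid must be collected for these subjects as for the rest. If Pecs-2 fails more often, the chance of the noninferiority claim falls (in the illustration, from 93.0% to 88.0% at 5% v 0%).

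Requiring both analyses to agree is the sponsor's option and costs more. On the same assumptions, the chance of the pain claim is then 88.6% at 10% failures in each arm and about 80% at 10% v 0%.

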Sample size justification. Power for the Wilcoxon-Mann-Whitney derived noninferiority testing is based on 10,000 simulated trials. We simulated pain scores from a discrete distribution with median (interquartile range) 3 (2-5).⁶ Between the quartiles, the probability of each score was assumed constant. The distribution for each group was assumed to be the same. The sample size of n=50 per group provides 82% power to detect noninferiority in pain with a margin of 1.25. Similarly, opioid consumption was assumed to follow a truncated normal distribution with mean 2.5 mg and standard deviation 2 mg, and minimum value 0 mg. The sample size of n = 50 per group provides at least 95% power to detect noninferiority with margin 2 mg. However, to account for any unanticipated increase in variability, we will enroll 25 additional subjects in each treatment group. Therefore, we will enroll 75 subjects for each of the two treatments with primary end point values for a total enrollment of 150 subjects with a primary end point. To allow for dropouts, we request a maximum enrollment of 175 subjects. Noninferiority in pain is tested first, and if significant, noninferiority in opioid consumption is tested. Under this hierarchical testing framework, no adjustment in alpha is necessary to control Type 1 error.⁷

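### The morning-after nausea score mixes how severe nausea was with whether the subject vomited; a re-anchored score and a separate vomiting item would make it readable

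*Combined protocol and SAP*

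**What the plan says.** Section 9 (Outcome measurements) sets one follow-up contact: "The morning following surgery, all subjects will be contacted by phone or in person [if hospitalized"]. Staff then "record lowest, average, highest, and current pain scores; sleep disturbances, and nausea". Nausea is scored as "nausea using a 0-10 Likert scale (0 = no nausea; 10 = vomiting"). Scores 1 to 9 have no anchors. Pain is asked in four forms at this contact. Nausea is asked once, and the text does not say whether the score is the worst, the average or the current level, or over what period.

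Vomiting is not listed as an outcome of its own. The nearest records concern treatment. In the recovery room, "pain scores, opioid requirements, and antiemetic administration will be recorded by nursing staff masked to treatment group". Later the plan adds: "In addition, we will extract antiemetic use from the electronic record".

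Nausea has no part in the primary claim, for which "both Hypotheses 1 and 2 must be at least non-inferior"; those hypotheses concern pain and opioid use. Section 9 (Statistical methods) names no test or margin for nausea. Only the general sentence "Descriptive statistics will be provided by arm and in aggregate" could cover it.

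**The concern.** A severity scale should run from none of a symptom to the most of that symptom. This one runs from no nausea to vomiting, which is related to nausea but is not its maximum. The same number can then describe different experiences, and a clearly worse night of nausea can receive a lower score than a mild one with a single emesis.

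Section 6 sets out to compare the risks as well as the benefits of the two blocks, and nausea is one of the few patient-reported tolerability outcomes. Subjects also go home with an oxycodone prescription. If the by-arm summaries of this score differ, a reader will want to know whether one block led to less nausea, less vomiting or both. The score alone does not answer that cleanly.

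**Working it through.** The plan gives no figure for nausea, so there is nothing to reproduce. The check is to apply the scale to plausible subjects and then to size the effect under stated assumptions.

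**Step 1. Apply the anchors.** The text can be read strictly (10 only for vomiting) or loosely (10 also for the most extreme nausea, since nothing else anchors it).

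| Subject | Strict | Loose |
|---|---|---|
| A: vomited once, otherwise well | 10 | 10 |
| B: severe nausea all night, no vomiting | at most 9 | up to 10 |
| C: vomited, with severe nausea all night | 10 | 10 |
| D: as A, but answers for how they feel at the call | possibly 0 | possibly 0 |

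- Strict reading: A ranks above B, and A and C cannot be told apart. The proportion scoring 10 gives vomiting incidence, and 0 to 9 orders severity among those who did not vomit.
- Loose reading: B may join A and C at 10, so the proportion scoring 10 overstates vomiting.
- Subject D arises because no recall window is given. In that case the proportion scoring 10 understates vomiting.

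The documents do not choose between these readings.

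**Step 2. Ask whether other records fill the gap.** Antiemetic records show treatment given, not emesis. They come from recovery-room nurses and the electronic record. Section 12 describes nearly all subjects as ambulatory, so most of the period up to the morning call is spent at home, where the chart is least likely to help.

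**Step 3. Size the effect on an arm mean.** Let p be the proportion who vomit and s the mean score those subjects would give on a pure severity scale. The shift caused by the anchor is p × (10 − s). Neither input is in the documents. Assume p = 10% and s between 7 and 9:

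- s = 9: 0.10 × (10 − 9) = 0.1 points
- s = 7: 0.10 × (10 − 7) = 0.3 points

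If s is the same in both arms, the shift in the group difference is (p₁ − p₂) × (10 − s). With equal vomiting it is zero. With 20% against 10%, it is again 0.10 × 1 = 0.1 to 0.10 × 3 = 0.3 points.

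**Step 4. See whether vomiting alone can move a rank comparison.** The plan specifies no such test for nausea, so this is only an illustration. It uses 75 subjects per arm and the same severity distribution in both arms (half score 0, the rest are spread evenly over 1 to 9). Vomiting is independent of severity and always scores 10. Over 3,000 simulated trials, the Wilcoxon-Mann-Whitney test gave p < 0.05 in 4.8% with vomiting at 10% in both arms, 20.7% with 10% against 20%, and 60.1% with 10% against 30%. A difference in the score can therefore arise with no difference in underlying severity.

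**Step 5. Trace what depends on the score.** The power statement, "The sample size of n=50 per group provides 82% power to detect noninferiority in pain with a margin of 1.25", rests on pain. The 2 mg margin concerns opioid use. The increase to 75 per group does not involve nausea either. All of these stay as they are.

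**The case against.** The strongest reply is that the anchor is a defensible composite in which vomiting is ranked as the worst state. Read strictly, it gives both pieces of information: the 10s count vomiting, and 0 to 9 order severity in everyone else. Antiemetic use gives a further check. The single-page case report form mentioned in Section 16 is not reproduced, so it may contain an item that the protocol does not list. No planned inference uses the score.

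Much of this stands, and it rules out three stronger readings that a reader might infer.

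- *The score measures neither severity nor vomiting incidence.* Not supported. On the strict reading it carries some of both; what it loses is severity among those who vomited.
- *The two can never be separated afterwards.* Not supported. Separation is possible on the strict reading and unreliable on the loose one, and the documents do not settle which applies.
- *With 10% vomiting, 1.0 point of each arm's mean is artefact (0.10 × 10).* Not supported. That treats every subject who vomited as having had no nausea at all (s = 0). With equal s, it also cancels from the group difference when vomiting is equal.

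The reply does not remove the practical problem. The strict reading works only if subjects and callers reserve 10 for vomiting and share one recall window. The protocol asks for neither.

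**Conclusion.** The point holds as a minor measurement weakness. The score mixes symptom intensity with an event, ranks a single brief emesis above severe nausea without vomiting, and loses severity for anyone who vomited. The proportion scoring 10 is an unreliable, though not empty, measure of vomiting incidence.

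Under the assumed inputs (10% vomiting, underlying severity 7 to 9) the shift in an arm mean is 0.1 to 0.3 points. It would be larger if vomiting were commoner or often came with little nausea. The documents give no rate for either, so this range is illustrative.

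Only a secondary tolerability outcome is affected, and the plan assigns it no rank, test or margin. Power, both margins, the enrolment target and the non-inferiority conclusion are unchanged.

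**What to change.** In Section 9 (Outcome measurements), and on the case report form:

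1. Anchor 10 as *worst nausea imaginable*, keeping 0 as none.
2. Ask for the worst nausea since leaving the recovery room, so that the score has a defined window.
3. Add one yes/no item, *any vomiting since leaving the recovery room*, covering the same window.
4. State that the score and the vomiting item will each be summarised separately by arm. The existing provision for descriptive statistics is enough; no new test is needed.

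The cost is one changed anchor and one extra question in a contact that already takes place. One limit remains: vomiting inside the recovery room falls outside the new window and would still be reflected only through antiemetic administration. If the change is made after enrolment has begun, scores collected under the two anchors should not be pooled as one scale.

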1. PROJECT TITLE

A Randomized, Subject-Masked, Active-Controlled, Parallel-Arm Clinical Trial Comparing Pecs-2 and Paravertebral Nerve Blocks

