6. SPECIFIC AIMS

The overall objective of the proposed research is to determine the relative risks and benefits of Pecs-2 versus paravertebral blocks for single-injection local anesthetic administration.

Hypothesis 1: Following breast surgery, **analgesia** will be non-inferior in the recovery room with a Pecs-2 block compared with a paravertebral block as measured with the Numeric Rating Scale.

Hypothesis 2: For breast surgery, **opioid** consumption will be non-inferior in the operating and recovery rooms with a Pecs-2 block compared with a paravertebral block (primary: cumulative intravenous morphine equivalents).

Primary end point: *In order to claim that Pecs-2 blocks are non-inferior to paravertebral blocks, both Hypotheses 1 and 2 must be at least non-inferior.*

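### Does calling the test block 'serratus' in the primary analysis leave the Pecs-2 comparison without a prespecified test?

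*Combined protocol and SAP*

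**What the plan says.** The title describes a "Parallel-Arm Clinical Trial Comparing Pecs-2 and Paravertebral Nerve Blocks". Section 9 randomises subjects to two groups: "1) Pecs-2 or (2) paravertebral block". Hypothesis 1 concerns pain control and predicts that it "will be non-inferior in the recovery room with a Pecs-2 block compared with a paravertebral block as measured with the Numeric Rating Scale". On opioids, the second hypothesis predicts that "consumption will be non-inferior in the operating and recovery rooms with a Pecs-2 block compared with a paravertebral block". Section 6 sets the rule for success: "In order to claim that Pecs-2 blocks are non-inferior to paravertebral blocks, both Hypotheses 1 and 2 must be at least non-inferior".

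The Statistical methods in section 9 use another name for the test block, in three places:

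- the opening of the primary aim: "We will test the noninferiority of the serratus nerve block compared to the paravertebral nerve block";
- the pain contrast, defined as the "group difference (paravertebral minus serratus) in median pain scores within the recovery room", with non-inferiority concluded if the lower 95% confidence limit lies above -1.25;
- the opioid test: "The noninferiority of the serratus nerve block with regard to total opioid consumption within the operating and recovery rooms", to be assessed in the same way as pain against a margin of 2 mg.

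These paragraphs never use the name Pecs-2. The documents do not define a serratus block or equate one with Pecs-2. Elsewhere the word occurs only for the serratus anterior muscle, the landmark for one of the two injections that make up the Pecs-2 block.

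**The concern.** These paragraphs give the decision rule that determines whether the trial succeeds, and they are the only place that states its direction. A confirmatory rule should identify the randomised arms. Here the test arm is misnamed in all three statements, for both co-primary end points. On a strictly literal reading, no subject receives the block being tested, and the Pecs-2 claim in section 6 has no matching analysis.

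A second worry follows. If the wording belonged to some other comparison, the margins beside it (1.25 points and 2 mg) might belong to that comparison too. At stake would be whether the primary tests and their margins were really prespecified for Pecs-2 against paravertebral block.

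**Working it through.** The point is textual, so the main check sets the sections side by side. The power figures are then checked for any dependence on the name.

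**1. Which arm can the word mean?** Section 9 has two groups, Pecs-2 and paravertebral. The Statistical methods name paravertebral correctly and subtract the other group from it. With one of two groups identified, the other is Pecs-2.

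**2. Do the end points match?**

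| Element | Hypotheses (sections 6 and 9) | Statistical methods (section 9) |
|---|---|---|
| Pain | Recovery room, Numeric Rating Scale | Recovery room pain scores |
| Opioid | Operating and recovery rooms, cumulative | Operating and recovery rooms, total |
| Comparator | Paravertebral | Paravertebral |
| Test block | Pecs-2 | Serratus |

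Only the last row differs.

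**3. Does the direction fit?** Let D = paravertebral minus test block. If the test block gives more pain, D is negative; a test block worse by 1.25 points gives D = -1.25. Requiring the lower 95% limit of D to exceed -1.25 therefore rules out a test block worse by the margin or more. That is the correct rule for Hypothesis 1 with Pecs-2 as the test block. The opioid margin is printed without a sign, but the test is to be done as for pain. Higher consumption on the test block again makes D negative, so the limit is -2 mg.

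**4. Are the margins tied to this trial?** The Sample size justification restates both margins (1.25 points and 2 mg), names the Wilcoxon-Mann-Whitney non-inferiority test, and fixes the order (pain, then opioid). It adds 25 to the 50 per group: 50 + 25 = 75, and 2 x 75 = 150 with a primary end point, with at most 175 enrolled. Section 10 repeats the 175. The word serratus does not occur there. The source cited for the pain distribution is, by its title, a study of single-injection paravertebral block, the comparator in this trial.

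**5. Does any figure depend on the name?** The power simulation assumes the same distribution in both groups and names no block. It was re-run with the 95% interval that goes with the rank test, counting success when the lower limit lies above minus the margin.

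- *Pain.* Inputs: median 3, interquartile range 2 to 5, margin 1.25, n = 50 per group. The plan does not fully define the distribution. The reading used puts 25% evenly on 0 to 2, 25% on 3, 25% on 4 to 5 and 25% on 6 to 10; this is an assumption. Power over 5,000 simulated trials was 81%, against 82% stated. Other readings gave 73% to 87%. At n = 75 per group the first reading gives 93%.
- *Opioid.* Inputs: normal with mean 2.5 mg and SD 2 mg, truncated at 0, margin 2 mg, n = 50 per group. Power over 3,000 simulated trials was above 99%, consistent with the stated 95% or more.

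Reading Pecs-2 for serratus enters none of these calculations, so the change in each result is zero.

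**The case for a change.** The best case for acting is that the slip sits in the sentences that decide the trial. It contradicts the title, the hypotheses and the randomisation text, and it could be corrected at almost no cost before unmasking. The opioid margin also lacks a sign, so its direction rests entirely on the misnamed pain contrast. No rationale is given for either margin and there are no pilot data, so one might want a sentence confirming that both were chosen for Pecs-2.

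Parts of this stand. The word is wrong, it is not a defined synonym, and it is not an artefact of text extraction. The margins do lack a stated rationale. The consequences do not follow, however. The contrast can be read in only one way, and the opioid direction follows from the pain rule. A signed limit would write down what the plan already implies. Whether 1.25 points and 2 mg are clinically justified is a separate question, and the answer would be the same had the text said Pecs-2 throughout. The documents do not show where the word came from. Copying from another comparison is one possibility; loose shorthand is another, since 20 of the 30 mL per side in the Pecs-2 block is placed above the serratus anterior muscle. Neither can be established, so doubt about the margins cannot rest on it.

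**Conclusion.** This is a clerical naming slip, repeated three times, with no effect on the analysis. An analyst with the randomisation list and the two hypotheses would compute paravertebral minus Pecs-2, compare the lower 95% limits with -1.25 points and then -2 mg, and require both to pass. No other contrast is available in a two-arm trial. The tests, margins, confidence level, sample size, power and possible conclusions are the same under either word, so no change to the plan is needed.

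The conclusion rests on there being only two randomised groups, on the end points and windows in the hypotheses matching those in the analysis text, and on the sample size text using the same two margins for this trial. It does not rest on the power re-run, whose pain figure depends on how the assumed distribution is read. It takes no position on whether the margins are clinically well chosen.
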